7.2.3 Demographic and Other Baseline Characteristics

Demographic and other baseline characteristics will be summarized using descriptive statistics.

Descriptive statistics for age, height, weight, and body mass index (BMI) at study entry will be presented. Frequency tabulations for sex, ethnicity and race will be shown. These summaries will be displayed for the SAF.

Medical history is coded in MedDRA and will be summarized by System Organ Class (SOC) and Preferred Term (PT) as well as by PT alone, for the SAF.

7.2.4 Concomitant Medications

Concomitant medications will be summarized by therapeutic subgroup (ATC 2nd level), chemical subgroup (ATC 4th level) and preferred WHO name. Subjects taking the same medication multiple times will be counted once per medication. A medication is classified into a single ATC based on the indication. Previous and concomitant medications will be listed.

7.3 Study Drug Exposure and Compliance

7.3.1 Exposure

The number of subjects immunized and whether or not the full dose was administered will be summarized by treatment group (ASP3772 (1 μ g, 2 μ g, 5 μ g) or PCV13) and stage. Since this is a single dose vaccine study, duration of exposure does not apply.

7.3.2 Treatment Compliance

Since this is a single dose vaccine trial, compliance does not apply.

7.4 Analysis of Immunogenicity

7.4.1 Analysis of Immunogenicity Endpoints

Assessment of immunological response following ASP3772 administration relative to PCV13 is a secondary objective for this study.

Stage 1, Group 1 and Stage 2, Group 2:

The objective in Stage 1, Group 1 and Stage 2, Group 2 is to determine if ASP3772 stimulates an immunogenic response to the 13 pneumococcal serotypes that are also contained in PCV13 and to determine if ASP3772 stimulates an immunogenic response to an additional 11 serotypes contained in ASP3772. The following summaries will be given by treatment group (ASP3772: 1, 2, 5 μ g vs. PCV13) and stage for all serotypes.

OPA Titer

- GMT, GSD and 95% CI
- The ratio of the OPA GMT (each ASP3772 dose level/PCV13), the GSD and 95% CI for the ratio
- The GMFR relative to baseline, GSD and 95% CI
- The proportion of subjects with a $>$ 4-fold increase in OPA titer¹

IgG Concentration

- The GMC, GSD and 95% CI
- The ratio of the IgG GMC (each ASP3772 dose level/PCV13), the GSD and 95% CI
- The GMFR relative to baseline, GSD and 95% CI
- The proportion of subjects with a \geq 4-fold increase in anticapsular PS IgG

Values below the LLOQ will be set to $\frac{1}{2}$ LLOQ for calculation of geometric means and set to LLOQ for calculation of fold changes.

Summaries for Stage 2 subjects will be given for 65-85, 65-74 and 75-85-year olds.

An analysis of covariance (ANCOVA) model with age (65 to 74 years, 75 to 85 years) as the covariate and treatment (ASP3772 1, 2, 5 μ g) as the factor of interest will be conducted on the natural logarithm (log) of pneumococcal OPA titers and on the natural log of the IgG concentrations for each serotype to examine dose response. Provided the treatment effect is

significant, paired comparisons between the 5 μ g vs 1 μ g, followed by 5 μ g vs 2 μ g, followed by 2 μ g vs 1 μ g will be conducted. There are no adjustments to control for the Family-Wise Error Rate (FWER) for 3 comparisons for each of the 24 serotypes. A Cochran-Armitage trend test will be used to test for trend.

CCI

Stage 2; Group 3:

The objective for Stage 2, Group 3 is to obtain estimates of the immune response following PPSV23 for the 11 serotypes contained in PPSV23 and not in PCV13. Immunological response 30 days after administration of PPSV23 will be summarized as follows:

- The GMT, GSD and 95% CI for the OPA titers
- The GMC, GSD and 95% CI for serotype-specific IgG levels.
- The GMFR, GSD and 95% CI in anticapsular polysaccharide IgG and OPA titer
- The number and percentage of subjects with a \geq 4-fold increase in anticapsular PS IgG and OPA relative to baseline.

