Stage 2 of the study is a dose-finding (sequentially higher doses), active-controlled, observer-blinded study with a 3:1 randomization (ASP3772:PCV13) in elderly subjects 65 to 85 years of age (Group 2). For Stage 2, Group 2 subjects the vaccine administrator will differ from the person evaluating reactogenicity to remove reporting bias for these events. Treatment assignment will also be unknown to the blinded study team.

After screening, PCV13 naïve subjects will be randomized within each cohort to receive ASP3772 or PCV13. Subjects randomized to ASP3772 will receive a single dose of ASP3772 administered as a 0.5 mL intramuscular (IM) injection on day 1, at 1 of 3 dose levels: 1, 2 or 5 µg of ASP3772 for Cohorts 4, 5 and 6, respectively. The subjects randomized to PCV13 will receive a single injection of the standard dose of PCV13.

Stage 2 will commence after the DEC has evaluated safety (including reactogenicity) data through 30 days from all cohorts in Stage 1. Dose escalation to Cohort 5 (intermediate dose, 2 µg) in Stage 2 will commence once the DEC has evaluated Stage 2 Cohort 4 (1 µg) safety (including reactogenicity) and tolerability through 7 days postimmunization. Dose escalation into Cohort 6 (high dose, 5 µg) in Stage 2 will commence once the DEC has evaluated Stage 2 Cohort 5. The DEC will review the data for each cohort in Stage 2, Group 2 in a blinded manner. The DEC Charter will provide details for revealing the treatment assignment for individual subjects to DEC members, if necessary. Randomization for Stage 2 subjects will be stratified by age (65 to 74 years of age and 75 to 85 years of age) to ensure there is a balanced number of subjects within each age cohort immunized with either ASP3772 or PCV13.

Safety and tolerability assessments including adverse events (AEs) will continue through 30 days postimmunization. Safety assessments for SAEs and MAAEs including PIMMCs and NOCDs will continue through day 180 postimmunization. Data will be collected in an observer-blinded manner (vaccine recipients and the site staff who are responsible for evaluation of any study endpoint will be unaware of which vaccine the subject received).

Serum samples to measure IgG and OPA will be collected prior to study vaccination on day 1 and postimmunization on day 30. The primary immunogenicity evaluation for dose finding is 30 days following the initial immunization.

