3.3 Randomization

A central randomization will be used for this study. Stage 1 subjects will be randomized to receive either ASP3772 (1, 2 or 5 µg) or PCV13 with a 3:1 ratio.

Stage 2, Group 2 subjects will be randomized to receive either ASP3772 (1, 2 or 5 µg) or PCV13 with a 3:1 ratio. The randomization for Group 2 will be stratified by age (65 to 74 years of age and 75 to 85 years of age).

The randomization assignment for Stage 1 and Stage 2, Group 2 will be unavailable to anyone involved with the study with the exception of the pharmacist and vaccine administrator until all Day 30 visits have been completed. After all subjects in Stage 1 have completed Day 30, there will be a data cutoff and an interim analysis. Similarly, once all Day 30 visits for subjects in Stage 2, Group 2 have completed, there will be a data cutoff and interim analysis. Additional safety information will be collected at the Day 180 visit.

Stage 2, Group 3 subjects will have been previously given PCV13 before entering the study and will be enrolled to receive a booster vaccination with PPSV23 only on Day 1.

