10 APPENDICES

10.1 Appendix A: Instructions to calculate the Summary statistics for the secondary endpoints

Geometric Mean (GM) and Geometric Standard Deviation (GSD)

To obtain the GM and GSD, first calculate the natural log of each titer or IgG concentration using the LOG function in SAS. Using PROC FREQ on the log transformed values obtain the mean and standard deviation of the log transformed values. Exponentiate mean and standard deviation to obtain the geometric mean and geometric standard deviation.

To obtain the lower confidence limit of the 95% confidence interval of the GM obtain the critical value of the student's distribution using TINV(0.975, n-1) where n=the number of non-zero titers or concentrations. For example, TINV(0.975, 19) = 2.093. The lower 95% confidence interval is then:

$$GM / GSD^{(TINV(0.975, n-1) / SQRT(n))}$$

and the upper 95% confidence is calculated using: $GM \times GSD^{(TINV(0.975, n-1) / SQRT(n))}$

where SQRT is the square root.

Geometric Mean Ratio (GMR)

To obtain the geometric ratio, calculate the GM for each treatment group. The geometric mean ratio can then be calculated as;

$$GM_{ASP3772} / GM_{PCV13}$$

Alternately, calculate the natural log of each titer or IgG concentration using the LOG function in SAS to transform the titers or IgG concentrations. Obtain the mean of the log transformed values for each treatment group, μ_1 and μ_0 . To calculate the geometric mean ratio:

$$GMR = e^{(\frac{\mu_1 - \mu_0}{2})}$$

where μ_1 is the arithmetic mean of the log transformed ASP3772 titers (or concentrations) and μ_0 is the arithmetic mean of the log transformed PCV13 titers (or concentrations).

To test that the null hypothesis that the GMR = 1, use the two sample t-test for the treatment difference of the log transformed titers (or concentrations). This is equivalent to testing if the GMR is equal to 1.

To obtain the 95% CI for the geometric mean ratio:

- (1) Obtain the standard error of the difference for the log transformed values SE_{DIFF} .
- (2) Calculate the lower CI:

$$e^{\frac{GMR - (TINV(0.975, n(1)+n(2)-2)) * SE_{DIFF}}{n(1)+n(2)-2}}$$

- (3) Calculate the upper CI:

$$e^{\frac{GMR + (TINV(0.975, n(1)+n(2)-2)) * SE_{DIFF}}{n(1)+n(2)-2}}$$

Geometric Mean Fold Increase (GMFR)

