To obtain the GMFR, calculate the fold rise for each subject. Take the natural log using LOG function in SAS. Using PROC FREQ on the log transformed values obtain the mean and standard deviation of the log transformed values. Exponentiate mean and standard deviation to obtain the geometric mean and geometric standard deviation.

To obtain the lower confidence limit of the 95% confidence interval of the GMFR obtain the critical value of the student's distribution using TINV (0.975, n-1) where n=the number of subjects. For example, with 20 subjects TINV (0.975, 19) = 2.093. The lower 95% confidence interval is then:

$$GM / GSD^{(TINV(0.975, n-1) / SQRT(n))}$$

and the upper 95% confidence is calculated using: $GM \times GSD^{(TINV(0.975, n-1) / SQRT(n))}$

where SQRT is the square root.

Comparing the Geometric Mean Fold Rise (GMFR) between two groups

To compare the GMFR between the two treatment groups (each dose of ASP3772 vs. PCV13) use an analysis of covariance with the log-transformed post immunization value as the dependent variable and the log-transformed pre vaccination value as the independent value. With log-transformed antibody values (titer or IgG levels) the variability usually decreases with increasing antibody values (heteroscedasticity).

Assume heteroscedasticity exists and use the following model to analyze the data.

```
proc mixed;  
  model y=group x group*x/ solution; repeated / local=exp ( x x2);  
  run;
```

Where: y= log-transformed post immunization antibody titer (or IgG concentration)

x= log-transformed pre immunization antibody titer (or IgG concentration)

x2=(log-transformed pre immunization antibody titer (or IgG concentration))² group= treatment group

group*x= treatment group by pre immunization log-transformed antibody titer (or IgG concentration). If group*x is significant then there is heteroscedasticity.

Use the ESTIMATE and CL options in proc mixed to obtain the estimate of the baseline corrected mean fold ratio and the 95% confidence interval for the baseline corrected mean fold ratio. The ratio is the GMFI for ASP3772 / PCV13. The baseline-corrected geometric mean ratio of the two treatment groups is:

2^{β_1} where β_1 is the estimate of the treatment group effect obtained from the ANCOVA. The 95% lower confidence limit is then $2^{\beta(LCL)}$ and the 95% upper confidence interval is then $2^{\beta(UCL)}$ LCL and UCL are the 95% confidence limits obtained from the CL option in Proc Mixed.

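### The visible Stage 2 immunogenicity models leave out the Day 1 value or the age stratum, and the one baseline-adjusted model leaves its log base and evaluation point open

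*SAP*

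**What the plan says.** **Dose response.** SAP 7.4.1 specifies "An analysis of covariance (ANCOVA) model with age (65 to 74 years, 75 to 85 years) as the covariate and treatment" (1, 2, 5 µg) as the factor, fitted to ln OPA and ln IgG for each serotype. If the treatment effect is significant, 5 v 1, 5 v 2 and 2 v 1 µg follow. No Day 1 term appears. Protocol 7.4 also has no Day 1 term, but includes PCV13 in the factor.

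**Data available.** For Group 2, SAP 3.2 states "Serum samples to measure IgG and OPA will be collected prior to study vaccination on day 1", and SAP 7.7.2 makes that pre-dose value the analysis baseline. SAP 3.3 adds "The randomization for Group 2 will be stratified by age". Cohorts 4, 5 and 6 (1, 2 and 5 µg) open in sequence, and randomisation within each is ASP3772 versus PCV13.

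**GMR versus PCV13.** SAP 7.1 sends this to Appendix A, which says to "use the two sample t-test for the treatment difference of the log transformed titers". It is planned for ages 65-85 pooled and for each age band.

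**Baseline-adjusted comparison.** The Appendix A part on comparing GMFR between groups covers each dose versus PCV13, "with the log-transformed post immunization value as the dependent variable and the log-transformed pre vaccination value as the independent value". The terms are group, x (log Day 1) and group*x, with a variance model because "the variability usually decreases with increasing antibody values (heteroscedasticity". The ratio is 2 to a power that "is the estimate of the treatment group effect obtained from the ANCOVA", and the limits are treated likewise. No log base is given there. For the GMFR itself, Appendix A says "Take the natural log using LOG function in SAS".

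**Redactions.** All of SAP 7.4.3 (Dose Response), a block after the ANCOVA paragraph in 7.4.1, and three of the eight Version 2 revision items in section 8 are blacked out.

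**The concern.** The 5 v 1, 5 v 2 and 2 v 1 µg contrasts compare people enrolled at different times, so randomisation does not balance their Day 1 antibody. In these contrasts the Day 1 value does two jobs: it explains variance and it removes a measured difference between cohorts. Appendix A already treats baseline as relevant, but the visible text applies it only to the PCV13 comparisons.

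The pooled GMR omits the factor used to stratify the randomisation. The baseline-adjusted model omits it too, and two gaps in its specification could change the printed ratio: the log base and the baseline value at which the group contrast is taken.

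Immunogenicity is secondary, but SAP section 4 says the phase 3 dose and sample size will be determined from the Stage 2 responses. The size of these ratios and the width of their intervals therefore matter.

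**Working it through.** **Inputs from the documents.** 99 subjects per ASP3772 dose; PCV13 pooled 3 × 33 = 99; Group 2 total 3 × (99 + 33) = 396, which reproduces the plan's figure. The example critical value in Appendix A, TINV(0.975, 19) = 2.093, also reproduces. The interval widths behind n = 100 cannot be reproduced, because no GMT or GSD is printed.

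**Assumed inputs (not in the documents).** ln-scale SD 1.2; correlation r of ln Day 1 with ln Day 30 of 0.3-0.6; age effect 0.4 ln; 35% aged 75-85; share of Day 1 values below LLOQ 0-60%; Day 1 difference between cohorts 0.1-0.3 ln.

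**1. Precision from adding ln(Day 1).** The approximate width ratio is √(1 − r²): 0.954, 0.893 and 0.800 for r = 0.3, 0.45 and 0.6. A simulation (four arms of 99, 800 runs per cell) gives the width with age + ln(Day 1) divided by the width with age only:

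| Day 1 below LLOQ (set to ½ LLOQ) | r = 0.3 | r = 0.45 | r = 0.6 |
|---|---|---|---|
| none | 0.956 | 0.894 | 0.802 |
| 30% | 0.960 | 0.903 | 0.820 |
| 60% | 0.968 | 0.924 | 0.859 |

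Intervals narrow by about 3% (1 − 0.968) to 20% (1 − 0.802). Setting values to LLOQ instead gives 0.961/0.910/0.830 (30% below) and 0.972/0.934/0.879 (60%).

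For two arms of 99 the half-width is 1.97 × 1.2 × √(2/99) = 0.336, a fold factor of e^0.336 = 1.40. At r = 0.3 it becomes e^(0.336 × 0.956) = 1.38; at r = 0.6, e^(0.336 × 0.802) = 1.31.

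**2. Day 1 difference between dose cohorts.** With equal SDs the slope is about r, so the spurious ratio is about e^(r × shift): e^(0.3 × 0.1) = 1.03 to e^(0.6 × 0.3) = 1.20. Simulation (true ratio 1.0, 1,500 runs per cell) gives 1.02-1.20 unadjusted. Adjusted, it gives 0.99-1.01 with 0-30% below LLOQ and 1.01-1.04 with 60% below.

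**3. Age stratum in the pooled GMR.** Gain = 1 − √(1 − p(1 − p)d²/SD²). With p 0.3-0.4, age effect d 0.2-0.6 and SD 0.8-1.6, this is 0.2-7%.

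**4. Back-transform.** If beta is a difference in natural logs, 2^beta = e^(0.693 × beta):
- 2.0 prints as 2^0.693 = 1.62
- 1.5 prints as 2^0.405 = 1.32
- 0.5 prints as 2^(−0.693) = 0.62

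With half-width 0.336, 2.0 (1.43-2.80) prints as 1.62 (1.28-2.04). A ratio of 1 stays 1, so whether the interval excludes 1 does not change.

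**5. Evaluation point.** With group*x, the group effect depends on x. For an assumed slope difference of 0.1 and a mean Day 1 titre of 8 to 100, the ratio at log Day 1 = 0 and the ratio at the mean differ by a factor of 8^0.1 = 1.23 to 100^0.1 = 1.58.

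**6. Should PCV13 join the dose model?** PCV13 lacks 11 of the 24 serotypes, so its Day 30 value there should follow Day 1 closely. Simulations assumed slope 0.9 and residual SD 0.3-0.6 in the PCV13 arm, and SD 1.2 with r 0.3-0.6 in the dose arms. A four-arm common-slope model gave 0.91-0.93 coverage of nominal 95% dose-contrast intervals. It left roughly 2-5% bias after a 0.3 ln Day 1 shift. The three-dose model kept coverage at 0.94-0.96 with bias under 1%. HC3 standard errors restored coverage in the four-arm model (0.94-0.95) but did not remove the bias.

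**The case against.** - **Redaction.** The blacked-out section is titled Dose Response, and another block follows the ANCOVA itself. A reader might infer that the sponsor has no baseline-adjusted dose model. The documents do not support that: one could sit in either place. Only the visible ANCOVA can be criticised.
- **Day 1 and age are already used.** GMFR and four-fold-rise proportions use Day 1, Appendix A gives a baseline-corrected ratio against PCV13, and GMRs are planned within each age band. This stands, and it confines the point to the dose contrasts, the pooled 65-85 GMR and the omissions in the Appendix A model.
- **2^beta may be right.** With log2 it is. A reader might infer a definite error, but that subsection states no base. What stands is a mismatch with the only base named elsewhere. The 7.4.1 GMRs and the dose-versus-dose contrasts are not affected.
- **The group coefficient.** A reader might infer that the reported ratio is the one at a Day 1 value of 1. Appendix A tells the programmer to use ESTIMATE, which can take the contrast at any baseline. The evaluation point is therefore unstated rather than wrong.
- **PCV13 left out of the SAP ANCOVA.** This fits a model meant to examine dose response. The difference from Protocol 7.4 needs a note, but is not a defect.
- **Small at the low end.** At r = 0.3 the fold factor moves only from 1.40 to 1.38, and even a 20% shift lies inside an interval of about ±40%. This is fair; the case rests on low cost, not on a large guaranteed gain.

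**Conclusion.** The point holds for the visible text. The dose-response ANCOVA omits a collected baseline value in contrasts that randomisation does not protect. The pooled GMR omits the randomisation stratum and the Day 1 value. The baseline-adjusted model omits age and leaves its log base and evaluation point open.

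On the assumed inputs, adjustment for Day 1 is worth about 3-20% in interval width and guards against a 2-20% shift in a dose ratio; the age stratum adds 0.2-7% to the pooled GMR. The 2^beta effect (2.0 printed as 1.62) applies only if those logs are natural, and never to the test of ratio = 1. The documents give no SD, correlation or share below LLOQ, so all these sizes except the back-transform arithmetic are conditional.

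A reader might also infer that adjustment makes the dose contrasts as good as randomised. It does not: cohort remains confounded with dose, and only measured Day 1 differences are removed.

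**What to change.** 1. **Dose contrasts (SAP 7.4.1).** Keep the three-dose ANCOVA and add ln(Day 1) beside the age stratum, for all 24 serotypes. State one LLOQ rule for ln(Day 1), since the SAP has two: ½ LLOQ for geometric means and LLOQ for fold changes.
2. **Pooled 65-85 GMR.** For the 13 serotypes shared with PCV13, report it from a model with treatment, ln(Day 1) and age stratum. Keep crude and age-band GMRs as descriptive. For the 11 serotypes PCV13 lacks, do not put PCV13 in a common-slope model with the doses.
3. **Appendix A baseline-adjusted model.** Add the age stratum. State the log base and the matching back-transform (exp for natural log). If group*x is kept, take the contrast at the mean ln(Day 1). Say whether the existing variance model or robust standard errors are used.
4. **Limits of adjustment.** State that it removes only measured Day 1 differences. The by-cohort PCV13 summaries in SAP 6.1.2 remain the check on drift.

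**Cost.** SAP wording and one covariate already collected, ideally settled before the Stage 2 Day 30 unblinding described in SAP 7.6. Subjects with no Day 1 result drop from the adjusted models; the documents do not say how many to expect. With no Day 1 values below LLOQ, the precision gain is used up only if about 1 − 0.956² = 9% lack a result at r = 0.3, or 1 − 0.894² = 20% at r = 0.45. The margin is smaller if many values are below LLOQ.

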After all subjects complete dosing in Cohort 1 (low dose, 1 μ g of ASP3772 or PCV13), safety (including reactogenicity) and tolerability through 7 days postimmunization will be assessed by the DEC. Assessments of safety and tolerability by the DEC will occur prior to initiating the next dose group, Cohort 2 (2 μ g of ASP3772 or PCV13) and then Cohort 3 (5 μ g of ASP3772 or PCV13), based on safety and tolerability data through 7 days postimmunization.

Safety and tolerability assessments will continue through 30 days postimmunization. Safety assessments for serious adverse events (SAEs) and medically attended adverse events (MAAEs) including potential immune-mediated medical conditions (PIMMCs) and NOCDs will continue through day 180 postimmunization. Data will be collected in an observer-blinded manner (vaccine recipients and any site staff who is responsible for evaluation of any study endpoint will be unaware of which vaccine the subject received).

Serum samples to measure IgG and opsonophagocytic activity (OPA) will be collected prior to the first study immunization on day 1 and on day 30 postimmunization.

Stage 2 Group 2:

Stage 2 of the study is a dose-finding (sequentially higher doses), active-controlled, observer-blinded study with 3:1 randomization (ASP3772:PCV13) in elderly subjects 65 to 85 years of age.

After screening, PCV13 naïve subjects will be randomized within each cohort to receive ASP3772 or PCV13. Subjects randomized to ASP3772 will receive a single dose of ASP3772 administered as a 0.5 mL intramuscular injection into the deltoid muscle of the right or left arm on day 1, at 1 of 3 dose levels: 1, 2 or 5 µg of ASP3772 for Cohorts 4, 5 and 6, respectively. The subjects randomized to PCV13 will receive a single injection of the standard dose of PCV13.

Approximately 396 subjects will be enrolled in Stage 2 of the study; 132 subjects per cohort (ASP3772 n = 99 and PCV13 n = 33).

Stage 2 will commence after the DEC has evaluated safety (including reactogenicity) data through 30 days from all cohorts in Stage 1. Dose escalation to Cohort 5 (intermediate dose, 2 µg) in Stage 2 will commence once the DEC has evaluated Stage 2 Cohort 4 (1 µg) safety (including reactogenicity) and tolerability through 7 days postimmunization. Dose escalation into Cohort 6 (high dose, 5 µg) in Stage 2 will commence once the DEC has evaluated Stage 2 Cohort 5. Randomization for Stage 2 subjects will be stratified by age (65 to 74 years

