7.1 Sample Size

In Stage 1, approximately 120 evaluable adults 18 to 64 years of age are planned to be enrolled. This sample size in is considered sufficient to obtain preliminary estimates in a phase 1 study of safety and reactogenicity in the adult population, ages 18 to 64. In Stage 2, approximately 495 evaluable adult subjects from 65 to 85 years of age are planned to be enrolled. For each PCV13 serotype the OPA titer⁻¹ responses (geometric mean titer [GMT] and GSD) in subjects 60 to 64 years of age administered PCV13 (Source Prevnar13[®] label) were assumed to be representative of the response following immunization with ASP3772. The width of 95% confidence intervals for each serotype with 30, 100 and 150 subjects were calculated. A sample size of 100 subjects at each dose level treated with ASP3772 under these assumptions was considered sufficient to provide good estimates of OPA titer⁻¹ responses. The sample size and dose level for the phase 3 study will be determined based on the responses in Stage 2 elderly subjects.

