4 SAMPLE SIZE

In Stage 1, approximately 120 evaluable adults 18 to 64 years of age are planned to be enrolled. This sample size is considered sufficient to obtain preliminary estimates in a phase 1 study of safety and reactogenicity in the adult population, ages 18 to 64. In Stage 2, approximately 396 evaluable adult subjects from 65 to 85 years of age are planned to be enrolled to receive either ASP3772 or PCV13. For each PCV13 serotype the OPA titer¹ responses, Geometric Mean Titer (GMT) and Geometric Standard Deviation (GSD) in subjects 60 to 64 years of age administered PCV13 (Source Prevnar13® label) were assumed

to be representative of the response following immunization with ASP3772. The width of 95% confidence intervals for each serotype with 30, 100 and 150 subjects were calculated. A sample size of approximately 100 subjects at each dose level treated with ASP3772 under these assumptions was considered sufficient to provide good estimates of OPA titer⁻¹ responses. The sample size and dose level for the phase 3 study will be determined based on the responses in stage 2 elderly subjects. In Stage 2, Group 3 approximately 99 subjects are planned to be enrolled to receive PPSV23 to provide estimates of the response to non-PCV13 serotypes in an elderly population.

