6.1.2 Secondary Endpoint(s)

Stage 1, Group 1:

Surrogate markers used to assess the immunological response on day 30 for the 13 serotypes common to ASP3772 and PCV13 are:

- Functional OPA activity for each serotype characterized by an OPA titer⁻¹ response expressed as the reciprocal of the serum dilution that causes a 50% reduction in the colony-forming units
- Pneumococcal serotype-specific anticapsular polysaccharide PS IgG for each serotype.

Summaries of immune response 30 days after immunization in adults 18 to 64 years of age will be provided for each serotype by treatment group (ASP3772 (1 µg, 2 µg, 5 µg) or PCV13) and stage. All adult subjects treated with PCV13 will be combined into a single group. To assess similarity between the 3 cohorts of PCV13 subjects, summaries will be provided by cohort for the PS IgG levels and the OPA titers.

Endpoints used to assess the immunological response on day 30 for the 11 serotypes unique to ASP3772 (2, 8, 9N, 10A, 11A, 12F, 15B, 17F, 20B, 22F, 33F) are:

- Geometric mean fold rise (GMFR) in anticapsular PS IgG at 30 days relative to pre-immunization
- Proportion of subjects with a ≥ 4 -fold increase in anticapsular PS IgG
- Functional OPA activity for each serotype characterized by an OPA titer⁻¹ response

Stage 2; Group 2:

Endpoints used to assess the immunological response on day 30 are:

- Functional OPA activity for each serotype characterized by an OPA titer⁻¹ response
- Pneumococcal serotype-specific anticapsular PS IgG for each serotype for the 13 serotypes contained in PCV13
- For each of the 11 serotypes unique to ASP3772, the GMFR in anticapsular PS IgG at 30 days relative to pre-immunization
- For each of the 11 serotypes unique to ASP3772, the proportion of subjects with a ≥ 4 -fold increase relative to baseline in anticapsular PS IgG for ASP3772 and PCV13-treated subjects

For Stage 2, Group 2 summaries will be provided by treatment group (ASP3772 (1 μ g, 2 μ g, 5 μ g) or PCV13) for all subjects age 65-85, for subjects 65-74 and for those 75-85. Subjects treated with PCV13 in cohorts 4, 5 and 6 will be combined into a single dose group and summarized by age (65-85, 65-74 and 75-85). To assess similarity between the 3 cohorts of PCV13 subjects, summaries will be provided by cohort for the PS IgG levels and the OPA titers.

In addition, for ASP3772, the following endpoints will be assessed.

- Dose response in the OPA titer⁻¹ for ASP3772
- Dose response in the PS IgG antibodies for ASP3772

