All statistical comparisons will be made using two sided tests at the $\alpha=0.05$ significance level unless specifically stated otherwise and 95% confidence intervals will be provided. All null hypotheses will be of no treatment difference; all alternative hypotheses will be two-sided, unless specifically stated otherwise.

All data processing, summarization, and analyses will be performed using SAS®Version 9.1.3 or higher on Unix. Specifications for table, figures, and data listing formats can be found in the TLF specifications for this study.

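### SAP 7.4.1 plans age-adjusted dose-to-dose comparisons only for serotypes with a significant F-test; the adjusted ratios and intervals should be given for every serotype

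*SAP*

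**What the plan says.** SAP 7.4.1 fits, per serotype, an ANCOVA with age group (65 to 74, 75 to 85) and ASP3772 dose (1, 2, 5 µg) to log OPA titre and to log IgG. The dose-to-dose step is conditional. Its sentence opens "Provided the treatment effect is" and continues "significant, paired comparisons between the 5" µg and 1 µg doses, then 5 against 2, then 2 against 1. The next sentence reads: "There are no adjustments to control for the Family-Wise Error Rate (FWER) for 3 comparisons for each of the 24 serotypes". On level and intervals, SAP 7.1 says "All statistical comparisons will be made using two sided tests at the" 0.05 level and attaches 95% confidence intervals.

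The same SAP section also lists outputs that carry no significance condition and cover all serotypes:
- GMT or GMC, with GSD and 95% CI, by dose
- the ratio of each dose to PCV13, with 95% CI
- the GMFR, with 95% CI
- the proportion with a 4-fold rise
- a Cochran-Armitage trend test

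Stage 2 summaries are given for ages 65-85 and for each age stratum.

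Dose response in OPA and in IgG is a Stage 2 secondary endpoint (SAP 6.1.2, introduced by "In addition, for ASP3772, the following endpoints will be assessed"). Protocol 7.1 states the use: "The sample size and dose level for the phase 3 study will be determined based on the responses in Stage 2 elderly subjects". Protocol 7.4 plans the ANCOVA with PCV13 as a fourth level and sets no F-test condition on dose contrasts. SAP 7.4.3, titled Dose Response, and a block in 7.4.1 are redacted.

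**The concern.** In the readable plan, the conditional step is the only direct, age-adjusted contrast of one ASP3772 dose with another. Two problems follow.

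First, a non-significant F-test does not show that a lower dose does as well as a higher one. When doses look alike, the choice depends on how wide the interval for their ratio is. That is where the text stops short of promising one.

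Second, a contrast shown only because the F-test was significant has been selected for being large. When the true difference is modest, the ratios shown overstate it on average.

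Two design features add weight. The trial was sized on precision rather than power: SAP 4 says that the widths of 95% "confidence intervals for each serotype with 30, 100 and 150 subjects were calculated". Making the dose contrasts depend on a test for which no power is stated does not fit that rationale. Also, subjects are randomised within sequential cohorts. Age stratification therefore balances ASP3772 against PCV13 within a cohort, but does not by design balance one dose against another, so an age-adjusted dose ratio is worth having.

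**Working it through.** **Plan's own figures.** Protocol 2.2.1 gives "132 subjects per cohort (ASP3772 n = 99 and PCV13 n = 33"), so Group 2 is 3 × (99 + 33) = 396. With the 99 PPSV23 subjects, 396 + 99 = 495. Both totals match. The choice of about 100 per dose cannot be reproduced, because neither the GSDs nor a target width is in the documents. For scale, the SAP Appendix A formula GM ×/÷ GSD^(t/√n) gives these 95% CI factors for a single geometric mean:
- GSD 3: 1.51, 1.24 and 1.19 at n = 30, 100 and 150
- GSD 8: 2.17, 1.51 and 1.40 at the same n

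**Inputs.**
- From the documents: n = 99 per dose; two-sided 0.05; 24 serotypes × 2 assays = 48 analyses.
- Assumed: GSD 3, 5 or 8; true 5/1 ratio R of 1 to 3; log-normal values; the 2 µg mean on the log-dose line, ln R × ln 2/ln 5; age strata balanced across doses; no other cohort differences.

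**Method.** 200,000 simulated trials per setting. F = n × (variance of the three log means)/(pooled log variance), tested at 5% on 2 and 3 × 99 − 4 = 293 df. The 5/1 ratio is exp(mean log at 5 µg − mean log at 1 µg), averaged on the log scale over trials with a significant F.

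**Results.** Each cell gives the share of analyses with a significant F-test, then the mean 5/1 ratio in those analyses.

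| True 5/1 ratio | GSD 3 | GSD 5 | GSD 8 |
|---|---|---|---|
| 1.25 | 22.8%, 1.50 | 12.8%, 1.70 | 9.4%, 1.84 |
| 1.5 | 63.6%, 1.64 | 33.5%, 1.89 | 21.3%, 2.14 |
| 2 | 98.4%, 2.01 | 77.6%, 2.17 | 54.3%, 2.45 |
| 3 | 100%, 3.00 | 99.4%, 3.01 | 92.3%, 3.14 |

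If all 48 analyses had a true ratio of 1.5, the number without a pairwise comparison would be:
- GSD 3: 48 × (1 − 0.636) = 17.5
- GSD 5: 48 × (1 − 0.335) = 31.9
- GSD 8: 48 × (1 − 0.213) = 37.8

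With no true difference, the F-test is significant in 48 × 0.05 = 2.4 analyses on average. In those, the 5/1 ratio lies on average 1.32, 1.50 or 1.69-fold from 1 (GSD 3, 5, 8), and its nominal 95% CI covers the truth about 50% of the time.

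**Without the condition.** The simulated mean equals the true ratio and coverage is 95%. The CI factor is exp(t × ln GSD × √(2/99)), which is 1.36, 1.57 or 1.79 for GSD 3, 5 or 8.

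**The case against.** The strongest reply is that nothing needed to compare doses is withheld. Geometric means with GSDs are listed per dose for every serotype, overall and by age stratum, and SAP 7.1 includes n among the descriptive statistics. Dividing two geometric means gives the crude dose ratio, free of selection. An interval follows from the GSDs and n, and even the age-adjusted contrast could be rebuilt from the stratum cells. This stands. It means the information is recoverable, but by hand, for 3 × 24 × 2 = 144 ratios.

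The conditional sentence can also be read as an F-protected testing sequence, since the next sentence concerns error rates. The SAP nowhere says that estimates are hidden when F is not significant. That is fair. But SAP 7.1 attaches intervals to comparisons that are made, so an interval for a comparison that is not conducted is not promised.

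SAP 7.1 names each dose against PCV13, and post-dose against pre-dose for the unique serotypes, as the comparisons of interest, and none of these is conditional. True, but neither kind is a dose-to-dose contrast. The trend test is unconditional too, but Cochran-Armitage is a test for proportions and gives no ratio of titres.

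Finally, SAP 7.4.3 may already contain unconditional dose-response estimates. That cannot be ruled out.

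**Conclusion.** The point holds in a limited form. The readable SAP commits to age-adjusted pairwise dose comparisons only where the F-test is significant. Contrasts selected in that way are biased away from 1 when the true difference is modest. At a true 5/1 ratio of 1.5, the mean shown is 1.64, 1.89 or 2.14 for GSD 3, 5 or 8. All these sizes rest on assumed GSDs and true ratios, because the documents give none. The counts out of 48 further assume one common ratio and GSD.

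A reader might infer more, and the documents do not support it:
- That no dose ratio, or only a p-value, is available for the remaining serotypes. The unconditional geometric means and dose/PCV13 ratios contradict this.
- That shown ratios are exaggerated in general. The bias is negligible when power is about 98% or more: 2.01 against a true 2 at GSD 3, and 3.01 against a true 3 at GSD 5.
- That the phase 3 dose depends on the conditional comparisons alone. The protocol refers to Stage 2 responses broadly.
- That the plan has no other dose-response analysis. The section with that title is redacted.

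**What to change.** In SAP 7.4.1, state that the three age-adjusted dose ratios (5/1, 5/2 and 2/1 µg) with 95% CIs will be reported from the ANCOVA for all 24 serotypes and for both OPA and IgG, whatever the F-test result. Keep the F-test only as the condition for declaring a pairwise difference statistically significant, and label the intervals as unadjusted for multiplicity, in line with the present text. If the redacted 7.4.3 already provides these estimates, a cross-reference is enough.

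The change is about one sentence and needs no new data, since the fitted model already yields the estimates. The rule for claiming significance is unchanged. The cost is longer tables: 144 ratios in all.
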